## 1 PURPOSE OF EXTENDING THE STUDY

**The purpose of extending the study was to evaluate the efficacy of bleomycin-based electrochemotherapy in treating colorectal liver metastases in a phase II clinical study.**

The purpose will be achieved by:

- applying treatment in a controlled manner based on pre-clinical experience and the clinical experience of the ESOPE project;
- evaluating procedures and results achieved;
- preparing standardized procedures;
- disseminating these new approaches to treatment using written and audio-visual materials as well as by attending and organizing expert meetings.

**The study is designed as an institutional study (Institute of Oncology Ljubljana) conducted in cooperation with the Faculty of Electrical Engineering (University of Ljubljana), University Medical Centre Ljubljana and industrial partner, IGEA srl., Carpi, Italy, which will provide technical support for the study. An additional 15 patients who meet the inclusion criteria will be included in the extended part of the study.**

The study will be carried out within the P3-0003 "Razvoj in ovrednotenje novih terapij za zdravljenje malignih tumorjev" (Development and evaluation of new therapies for treating malignant tumours) research programme headed by [name], PhD.

## 2 STARTING POINTS

### *Principles of electroporation and electrochemotherapy (ECT)*

By exposing a cell to an external electric field, transmembrane voltage is established on the cell membrane. When the threshold value is exceeded, this voltage causes electroporation of the cell membrane, i.e. the formation of hydrophilic pores, which allow the increased passage of molecules into the cell.

The principle of electrochemotherapy (ECT) is based on exposing the tumour to electroporation pulses delivered by specific electrodes. This allows the passage of previously applied hydrophilic cytostatics, e.g. bleomycin and cisplatin, into cells. Because the intake of cytostatics is increased only in areas exposed to electroporation pulses, ECT is a local treatment method. In addition to the direct action of cytostatics on tumour cells, ECT has an indirect vascular-disrupting effect, because cytostatics act on the endothelial cells in tumour vasculature. Doses of cytostatics used in ECT are extremely low, resulting in minimal or no systemic toxicity. Furthermore, the application of electroporation pulses reduces blood flow in the tumour, which keeps the cytostatics in the tumour for a longer period of time, thus making the treatment more effective.

### *Clinical applications of ECT*

In the early 1990s, our team took an active part in pioneering clinical studies on treating cutaneous and subcutaneous tumours with ECT. According to the findings of these first clinical trials, 80% of objective responses of treated tumour nodules are achieved using ECT. Our team also helped draw up and publish standard surgical procedures for treating cutaneous and subcutaneous tumours using ECT. Today, ECT is a well-established method for treating malignant melanoma metastases, especially as part of palliative care, in 15 European countries. In 2011, 2,000 patients were treated with ECT and, according to several databases, ECT is now used in 100 oncology centres.

In the first recorded clinical case of treating a deep-seated tumour with ECT, melanoma metastases in thigh muscles were treated. Experience in treating other types of soft tissue tumours with ECT is good, but limited to a few clinical cases and studies involving a small number of patients. In addition to treating deep-seated soft tissue tumours, ECT is also used to treat deep-seated tumours in internal organs. Brain and liver metastases have already been shown to be effective targets in ECT.

### *Treatment of liver tumours*

Colorectal cancer is the most common cancer and the second most common cause of cancer death in Europe, taking into account both sexes. At the time of diagnosis, more than 23% of patients have liver metastases, while after the first treatment, metastases occur in a further 20% of patients. In Slovenia, the incidence of colorectal cancer metastases that are eligible for surgical treatment is from 12 to 15 per 100,000 population, and is higher than the incidence of other liver metastases. In these cases, radical liver resection is the only promising treatment method, having an almost 50% 5-year survival, but due to the scale of the disease, it is only feasible in a minority of cases. The distant form of the disease is usually treated with systemic chemotherapy or biological drugs, which are only partially successful while producing high systemic toxicity. Where individual small metastases are present, patients are offered a local form of treatment: a thermoablation method called radiofrequency ablation (RFA). Metastases that grow into the inferior vena cava or into the area of large hepatic and portal veins, and on which RFA has small or no effect due to cooling, are particularly problematic. Therefore, new, more effective approaches to liver metastases treatment are being sought for such patients.

A phase I/II clinical study is currently underway at Institute of Oncology Ljubljana to assess the safety and efficacy of treatment for colorectal liver metastases using ECT. We wish to include an additional fifteen (15) patients within phase II using this protocol. To date, 17 patients have been included in the clinical study, and preliminary results in 16 of these patients indicate that treating colorectal liver metastases and one HCC patient using ECT is a safe method for treating tumours even in hard-to-reach locations. Preliminary MRI results in all patients testify to radiological changes similar to those observed after RFA treatment. The response to ECT treatment was complete in 50% of patients and partial in the remaining 50% of patients. Preliminary histological analysis results for all ECT-treated metastases after surgical removal indicate progressive degenerative changes within metastases and a statistically significant reduction in viable tumour tissue in ECT-treated metastases compared to non-ECT-treated metastases ( $p < 0.001$ ). We were the first to publish the technological part of the procedure in the clinical case.

### *Planning ECT treatment*

ECT treatment of deep-seated tumours in internal organs requires planning based on diagnostic radiology imaging. Electrode type is selected based on the precise location and measured size of the

tumour nodules; for metastases located up to 3 cm (lower edge of the metastasis) below the liver surface, which are more easily accessible to ECT, short needle electrodes with a fixed hexagonal geometric arrangement are appropriate, while for hard-to-reach and deep-seated metastases, long needle electrodes with an arbitrary geometric arrangement have recently been made available. In line with technological advances and the development of new electrode types, experts at the Italian company IGEA designed a new electric pulse generator called the Cliniporator VITAE for treating larger and deep-seated tumours, such as liver metastases. The generator meets the essential requirements for consumer safety, and health or environmental protection as defined by EU guidelines or regulations, as it has the CE mark.

The distribution of the electric field within the tissue is an important predictor for the success of ECT tumour treatment, as the change in the transmembrane potential of the cell membrane, which is a prerequisite for successful electroporation, is directly proportional to the electric field strength. Numerical modelling is currently the only effective method for predicting electric field distribution in tissue, as its structure is, by definition, inhomogeneous, nonlinear, and in some cases anisotropic. When using long needle electrodes with an arbitrary geometric arrangement, it is necessary to determine the depth of electrode insertion into the tumour nodule, and the voltage, length and frequency of the supplied electroporation pulses based on numerical modelling in order to achieve optimal coverage of tumour nodules with an electric field.

#### *Electroporation pulse synchronization using electrocardiogram (ECG)*

In ECT treatment, the electric current reaches the surroundings of the treated area due to the high electrical conductivity of the tissue. This increases the likelihood of possible interaction between electroporation pulses and heart function when treating deep-seated tumours in internal organs due to the anatomical proximity of the heart. In our clinical study, we used a synchronization procedure built into the electroporation pulse generator (Cliniporator VITAE) to avoid cardiac dysfunction caused by ECT. So far, this procedure has proven to be effective in preventing cardiac pacing during the ventricular sensitivity period. Nevertheless, further research is urgently needed to verify the effectiveness of the existing synchronization procedure and to determine any short- or long-term effects of electroporation pulses on heart function.

Preliminary results suggest that ECT does not seriously affect cardiac function, but there are statistically significant changes in some parameters of heart rate variability during and after therapy relative to pre-therapy parameter values.

### 3 PATIENT SELECTION

The suitability of patients for inclusion in the study will be assessed using inclusion and exclusion criteria.

#### 3.1 Inclusion criteria

1. Patients with one to three (1–3) metachronous colorectal liver metastases, up to 5 cm in size, that are difficult to resect due to their position (likelihood of insufficient healthy liver after resection) or inaccessible for treatment with standard ablation techniques because they are located on large hepatic vascular structures (portal veins, hepatic veins or their inflow into the inferior vena cava, immediate vicinity of vena cava), but are otherwise operable.
2. Patients with up to three (3) recurring colorectal liver metastases, each with a maximum diameter not exceeding five (5) cm, and for which other treatment is either unacceptably risky due to possible insufficient residual liver volume after resection or expected to be less effective due to the proximity of veins in RFA.

*Patients in groups 1 and 2 are patients in whom standard treatment options (systemic and/or surgical) have been exhausted. ECT will be offered to these patients as the only therapeutic option. If a patient has a large number of metastases that are unresectable and at the same time unsuitable for RFA, the metastases will be treated with ECT, while any other metastases will be resected or treated with RFA.*

3. Patients with synchronous colorectal liver metastases, in whom—due to their poor general health or the extent of the disease—first the removal of the primary tumour is planned, and after 2–3 months, surgery on the metastases, with systemic treatment taking place in the meantime. ECT would be used to treat metastases up to 5 cm in maximum diameter during the first surgical procedure, i.e. when the primary tumour is removed.
4. Patients with bilateral metachronous colorectal liver metastases who require two-stage surgery due to the extent of the disease, i.e. right portal vein ligation and excision or RFA of metastases in the left hepatic lobe at the first stage and right hepatic lobe resection at the second stage. During the right portal vein ligation surgery, the metastases should be accessible in order to apply electroporation pulses without major manipulation and mobilization of the liver, so as not to create additional problems for the second planned procedure, i.e. the removal of metastases by resecting the right hepatic lobe.

*Patients in groups 3 and 4 are potentially curable using standard treatment. The fact that these patients will be operated on twice as part of standard treatment will be used to apply ECT during the first procedure and to resect treated and untreated metastases during the second. The added ECT used on these patients will not affect the standard treatment recommended in the current guidelines.*

5. The patient is offered ECT treatment even if the patient refuses standard treatment options.
6. Histologically and/or cytologically confirmed colorectal cancer.
7. Age above 18.
8. Life expectancy over 3 months.
9. Performance status (PS)  $\geq 70$  according to Karnofsky PS or  $\geq 2$  according to WHO recommendations.
10. Depending on the type of active substance, 2–5 weeks have passed since the last treatment, if any.

11. The patient must understand the treatment process and any side effects.
12. The patient must be able to give consent to participate in a clinical trial ('informed consent').
13. Prior to inclusion in the study, the patient should be treated by a multidisciplinary gastrointestinal tumour team.

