## 5 TREATMENT: ELECTROCHEMOTHERAPY (ECT)

Patients with multiple bilateral metastases scheduled for two-stage surgery depending on their general condition and extent of the disease will have their right portal vein ligated and up to 3 metastases treated on the right hepatic lobe with up to 3 cm in maximum diameter using ECT during the first surgical procedure. On the left, metastases will be treated using established methods, such as surgery and RFA. During the second procedure, the entire right half of the liver will be removed.

In patients with liver metastases in areas where, due to the proximity of the main hepatic veins, surgery is not possible and the success of other ablation techniques cannot be predicted, ECT will be performed.

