### 6.1. Effects of treating colorectal liver metastases using ECT

- Early treatment effects will be assessed using DCE-US or CT based on changes in tumour blood flow after ECT compared to pre-ECT blood flow.
- Late effects will be assessed based on modified RECIST criteria, taking into account the change in the size and density of treated tumour nodules before and after ECT. These will be assessed based on DCE-MRI images; the volume of the metastases will be calculated using the formula  $V = \frac{a \times b^2 \times \pi}{6}$ , where a is the shorter and b the longer metastasis diameter.

Based on the assessment of the late ECT effects, the response to treatment will be evaluated in line with the WHO classification:

- Complete response (CR): complete disappearance of the tumour nodule
  - Partial response (PR): reduction of tumour nodule size by more than 50%
  - No change (NC): decrease in tumour nodule size by less than 50% or increase in tumour nodule size by less than 25%
  - Progressive disease (PD): growth of the tumour nodule by more than 25%
- The direct effect will be assessed by histological analysis of those metastases that will be surgically removed.
  - EORTC Quality of Life questionnaire according to QLQ C30 standards

EXAMINATION/TEST	Screening period until D -14	D -1	D 7	D 30	D 60	D 90	D 120
clinical examination, anamnesis	X	X	X	X	X	X	X
ECG	X	X					

DCE-MRI	X			X		X
DCE-US	X			X	X	X
CT perfusion	X			X		X
Blood count	X	X	X			
Coagulation tests	X	X	X			
Biochemical blood analysis	X	X	X	X	X	X
EORTC QLQ C30 questionnaire	X		X	X		

\*D = day

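### In group 3 the imaging response mixes ECT with systemic treatment, and in groups 3 and 4 the treated lesions are later resected; the response analysis has no rule for either

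*Combined protocol and SAP*

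**What the plan says.** Section 1 sets the purpose as to "evaluate the efficacy of bleomycin-based electrochemotherapy in treating colorectal liver metastases in a phase II clinical study". It adds 15 patients and gives no split by inclusion group.

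Section 3.1 defines groups that differ in what happens after ECT:

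- **Groups 1 and 2:** standard options are exhausted, and "ECT will be offered to these patients as the only therapeutic option".
- **Group 3 (synchronous metastases):** "ECT would be used to treat metastases up to 5 cm in maximum diameter during the first surgical procedure", when the primary is removed. Then comes, "after 2–3 months, surgery on the metastases, with systemic treatment taking place in the meantime".
- **Group 4 (two-stage surgery):** ECT is given at the first stage. Section 5 says of the second: "During the second procedure, the entire right half of the liver will be removed". No interval and no interim systemic treatment are stated.
- **Groups 3 and 4 together:** the two operations will be used to "apply ECT during the first procedure and to resect treated and untreated metastases during the second".
- **Item 5:** patients who refuse standard treatment may also be offered ECT.

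Section 6.1 bases late response on the change in treated nodules from before to after ECT on DCE-MRI, graded on the WHO scale, for example "Complete response (CR): complete disappearance of the tumour nodule". Lesions that are surgically removed also have a histological readout, and section 3.3 plans a treated-versus-untreated histological comparison in two-stage patients.

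Section 7 describes the antitumour effect without strata. Section 8 compares response only by tumour location.

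**The concern.** The response grading takes the change in a treated nodule as the effect of ECT. That is reasonable where ECT is the only treatment acting on the nodule. In group 3 it is not, because systemic treatment acts on the same nodule between ECT and the second operation. Shrinkage from either source is graded in the same way.

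A second problem applies to both two-stage groups. Once the treated lesion has been removed, a later scan carries no information about it. The plan does not say which scan counts, what to do with a lesion resected before a scan, or whether the groups are to be reported apart.

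Response has no control arm and only 15 patients are added. A few patients from groups 3 and 4 can therefore move an overall response rate or leave it partly unobserved, and the rate would no longer estimate what section 1 sets out to measure.

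**Working it through.** The plan gives no target response rate, null rate or sample-size calculation, so there is no figure of its own to reproduce. Three checks follow.

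**1. Timeline for group 3.** One month is 365.25/12 = 30.4 days. Two months is 60.9 days and three months is 91.3 days, so the second operation falls at about D61–D91. As extracted, the section 6.1 schedule has DCE-MRI at screening, D30 and D90; the table is broken, so the columns are uncertain.

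| Scan | Relation to group 3 second operation | Relation to systemic treatment |
|---|---|---|
| D30 | Before it | May already carry an effect; the start date is not given |
| D90 | At or after nearly the whole window | Carries the effect, if the lesion is still there |

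For group 4 no such table can be drawn, because the documents give no interval.

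**2. Size of the attribution bias in an all-patient rate.** Let f be the share of patients in group 3, r the response rate from ECT alone, and c the response rate from systemic treatment alone by the time of the scan, with the two acting independently.

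- Response in group 3: 1 − (1−r)(1−c) = r + (1−r)c
- All-patient rate: (1−f)r + f[r + (1−r)c] = r + f(1−r)c
- Bias: f(1−r)c

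The documents give none of these inputs for this purpose. Assume f from 1/3 to 1/2 and c from 30% to 60%.

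| r | Smallest bias (f = 1/3, c = 0.3) | Largest bias (f = 1/2, c = 0.6) |
|---|---|---|
| 0.40 | 1/3 × 0.6 × 0.3 = 0.06 | 1/2 × 0.6 × 0.6 = 0.18 |
| 0.60 | 1/3 × 0.4 × 0.3 = 0.04 | 1/2 × 0.4 × 0.6 = 0.12 |
| 0.80 | 1/3 × 0.2 × 0.3 = 0.02 | 1/2 × 0.2 × 0.6 = 0.06 |
| 0.90 | 1/3 × 0.1 × 0.3 = 0.01 | 1/2 × 0.1 × 0.6 = 0.03 |
| 1.00 | 0 | 0 |

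So the bias is 4–18 points for r of 40–60%, 2–6 points at 80%, and vanishes for objective response as r approaches 100%.

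**3. Late readings lost to resection.** Suppose k of 15 patients have no late scan because the lesion is gone, and half of the others respond. Counting the missing patients as all non-responders, then as all responders, bounds the rate:

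- k = 3: 6/15 to 9/15, or 40–60%
- k = 5: 5/15 to 10/15, or 33–67%

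**The case against.** The strongest objection uses the protocol's own results. Section 2 (Treatment of liver tumours) reports preliminary responses that were half complete and half partial, so every patient had an objective response. Section 2 (Clinical applications of ECT) gives 80% for treated nodules in the first clinical trials, on cutaneous and subcutaneous tumours. On those figures the bias in objective response is zero, or 2–6 points. This stands as a limit on the size. It does not dispose of the point: the preliminary figure is not broken down by inclusion group, so it may contain the same mixture, and systemic treatment can still turn a partial response into a complete one.

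Next, histology already compares treated with untreated metastases in two-stage patients. Where both kinds of lesion exist, systemic treatment acts on both, so this is a real partial control. It is a pathology readout, however, and leaves the imaging response as it is.

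A reader might also infer four stronger things that the documents do not support:

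- **That a resected nodule will be scored as a complete response.** Section 6.1 grades the measured change in the nodule and provides histology for removed lesions. Nothing suggests that surgical absence would be graded as CR.
- **That the plan prescribes one pooled rate.** It never says so. Pooling is inferred from the unstratified description and the single split by tumour location.
- **That late response is unobservable in groups 3 and 4.** A D30 scan precedes the group 3 second operation.
- **That group 4 is affected by systemic treatment.** None is stated for that group.

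**Conclusion.** The point holds as an attribution and missing-data problem. In group 3 the imaging response cannot be credited to ECT alone, and a scan near D90 will usually come at or after resection. In group 4 only the resection problem applies, and its timing is unknown.

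The size cannot be fixed from the documents, because group numbers, the ECT-alone response and the systemic-alone response are all assumptions. The plausible range runs from almost nothing, if ECT alone produces an objective response in nearly every patient, to 18 points at the far end of the assumed values. The calculation also assumes that an all-patient rate is reported and that the two treatments act independently.

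This is more than a missing detail: the plan as written gives no way to separate the two effects on imaging. It should be changed, and the change is confined to the analysis.

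**What to change.** 1. **Name the scan that counts.** Use the last DCE-MRI before any second operation (D30 for group 3, if the schedule is as extracted), and report its day. Class a lesion resected before a scan as not evaluable on that scan. This deals with resection but does not by itself remove a systemic effect already present at D30.
2. **Report response by inclusion group.** Give groups 1, 2 and 5 as the estimate least affected by planned systemic treatment and resection, groups 3 and 4 separately, and the all-patient rate as a secondary description. Groups 1 and 2 are not guaranteed free of later systemic treatment, so record any that is given.
3. **Use untreated lesions as a within-patient control.** In groups 3 and 4, where an untreated metastasis remains in place, read it on the same MRIs and report the treated-minus-untreated difference alongside the planned histology.

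**Cost.** Analysis wording and extra reading of scans already planned; no treatment, visit or patient number changes. The real price is precision. Exact 95% intervals are about 27–79% for 8 of 15 responders, 19–81% for 5 of 10, and 15–95% for 3 of 5, so the group 1, 2 and 5 estimate could be very imprecise. Untreated comparators will not exist in every patient: in group 4 the left-lobe lesions are excised or ablated at the first stage, and nothing guarantees one in group 3.

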### **3.2 Exclusion criteria**

1. Any previously confirmed form of cancer other than surgically treated non-invasive uterine cancer or basal cell carcinoma treated with surgery or radiotherapy.
2. Proven visceral and/or bone metastases or diffuse metastases.
3. Life-threatening infection and/or heart failure and/or liver failure and/or other life-threatening systemic conditions.
4. Ascites.
5. Significantly reduced lung function.
6. Age under 18.
7. Coagulation system disorders.
8. Received cumulative dose of bleomycin  $\geq 250 \text{ mg/m}^2$ .
9. Allergic reactions to previous treatment with bleomycin.
10. Chronic decrease in renal function (creatinine  $> 150 \text{ }\mu\text{mol/L}$ ).
11. Epilepsy
12. Heart rhythm disorders.
13. Implanted pacemaker or defibrillator.
14. Pregnancy.
15. Patients who are unable to understand the purpose of the study.

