### **3.3 Examinations and tests before treatment**

Two weeks before inclusion in the study, the following will be performed:

- clinical examination, anamnesis
- radiological imaging techniques to discover liver metastases:
  - dynamic contrast-enhanced magnetic resonance imaging (DCE-MRI)
  - dynamic contrast-enhanced ultrasound (DCE-US)
  - computed tomography (CT) perfusion
- Testing for systemic metastases
  - CT of the lungs
  - other examinations depending on the clinical picture (bone scintigraphy, PET/CT)

One week before inclusion in the study, the following will be performed:

- laboratory tests:
  - haematological tests with a complete blood count
  - coagulation tests
  - biochemical tests: electrolytes, creatinine, transaminases
  - immunohistochemical examinations: tumour markers
- ECG

In patients for whom two-stage surgery is planned, the following will be performed:

- histological analysis of liver metastases and comparison of pathohistological changes between treated and untreated metastases.

[figure not shown]

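### Inclusion criterion 9 sets both performance-status limits with the same inequality although the two scales run in opposite directions, so it does not work as a fitness limit

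*Combined protocol and SAP*

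**What the plan says.** Section 3.1, item 9, requires a performance status of at least 70 "according to Karnofsky PS or $\geq 2$ according to WHO recommendations". The same inequality is used for both scales and the halves are joined by *or*. The protocol defines neither scale, gives no conversion between them, and does not restate the limit anywhere else.

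Other criteria bear on fitness:
- Section 3.1, item 8: "Life expectancy over 3 months".
- Section 3.2, exclusion 3: "Life-threatening infection and/or heart failure and/or liver failure and/or other life-threatening systemic conditions".
- Section 3.2, exclusions 4, 5, 7, 10 and 12: ascites, markedly reduced lung function, coagulation disorders, raised creatinine and heart rhythm disorders.
- Section 3.1, group 1 only: the metastases are hard to resect or to ablate, "but are otherwise operable".

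Group 3 in section 3.1 covers patients whose staged surgery is explained by poor general condition or by disease extent.

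On a related wording matter, exclusion 2 in section 3.2 bars "Proven visceral and/or bone metastases or diffuse metastases" and makes no exception for the liver. Group 1 opens with "Patients with one to three (1–3) metachronous colorectal liver metastases", and groups 2 to 4 also require liver metastases.

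**The concern.** A limit of the form *at or above* sets a floor on fitness when the scale rises with fitness, as Karnofsky does. On a scale that falls with fitness, as the WHO scale does, the same form sets a ceiling. Item 9 therefore contains a floor and a ceiling joined by *or*, and the two cannot be equivalent versions of one rule.

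Two things are at stake. The first is screening: patients receive intravenous bleomycin and electroporation during surgery, and item 9 is the only criterion that measures general functional status. The second is description: section 7 plans a descriptive account of antitumour effect, adverse effects and quality of life, and eligibility says whom that account is about. With 15 additional patients planned (section 1), each patient is 1/15 = 6.7% of the extension, so a few patients admitted on an unintended reading would visibly change the group described.

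**Working it through.** The plan gives no figure to reproduce. This is a logic check of an eligibility rule.

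**Inputs**
- Rule (section 3.1, item 9): Karnofsky ≥ 70 *or* WHO ≥ 2.
- Assumption, from the standard definitions and not printed in the documents: Karnofsky runs from 100 (best) down to 10 in living patients; WHO runs from 0 (best) to 4 (worst).
- Assumption: three possible conversions, used because the protocol gives none.

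| Conversion | WHO 0 | WHO 1 | WHO 2 | WHO 3 | WHO 4 |
|---|---|---|---|---|---|
| A | 100–90 | 80–70 | 60–50 | 40–30 | 20–10 |
| B | 100 | 90–80 | 70–60 | 50–40 | 30–10 |
| C | 100–90 | 80 | 70–60 | 50–40 | 30–10 |

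**Step 1: the rule as printed.** The entries are Karnofsky levels.

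| Conversion | Pass under logical *or* | Pass on WHO half alone | Refused by WHO half alone | Pass both halves |
|---|---|---|---|---|
| A | 100–10 (10 of 10) | 60–10 (6 of 10) | 100–70 | none |
| B | 100–10 (10 of 10) | 70–10 (7 of 10) | 100–80 | 70 only |
| C | 100–10 (10 of 10) | 70–10 (7 of 10) | 100–80 | 70 only |

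To fail the logical *or*, a patient would need Karnofsky below 70 and WHO 0 or 1 at the same time. No level meets both conditions under any of the three conversions. Equivalent limits would pass the same levels, but here the two halves share no level or one.

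**Step 2: would turning the sign be enough?** Purely as an illustration, keep the printed digit and read the WHO half as WHO ≤ 2. The *or* rule then admits Karnofsky 100–50 under A and 100–60 under B and C. The lowest levels no longer pass, but levels below 70 still do, through the WHO half. The two limits would point the same way without corresponding to the same fitness level.

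**Step 3: what else screens for fitness?** Item 8 concerns prognosis. Exclusion 3 concerns life-threatening conditions. Exclusions 4, 5, 7, 10 and 12 each concern a specific organ or condition. Operability is stated for group 1 only. All of these remove some unfit patients, but none sets a level of general functioning.

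**Step 4: exclusion 2 beside the inclusion groups.** Groups 1 to 4 require liver metastases, and the liver is a viscus, so the literal wording collides with them. Section 3.3 lists imaging of liver metastases separately from "Testing for systemic metastases", where it names lung CT, bone scintigraphy and PET/CT. That suggests disease outside the liver was meant, although the criterion does not say so.

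**The case against.** The strongest reply is that this is a sign or translation slip with little practical reach. The Karnofsky half is coherent and shows the intent. The study runs at one institution, so one team applies the rule. Item 13 requires the multidisciplinary gastrointestinal tumour team to be involved before inclusion. Groups 3 and 4 receive electrochemotherapy during operations that standard treatment already calls for. Eligibility criteria apply jointly, so an empty item 9 leaves the others working. The text was also read from PDF by a program, so a misread symbol cannot be wholly ruled out.

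Much of this stands, and it limits what may be concluded:
- A reader might infer that the trial admits patients of any fitness. The documents do not support that: the other criteria still apply, and the statement is true of item 9 alone.
- A reader might infer that unfit patients have been enrolled. Nothing in the documents shows anyone admitted through the WHO half.
- A reader might infer that the item guards open liver surgery. The protocol describes treatment during surgery but does not call it open, and in group 3 the operation is removal of the primary tumour.
- A reader might infer that exclusion 2 leaves no eligible patient. That follows only from a literal reading that the inclusion groups and the work-up in section 3.3 make implausible.

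The reply does not rescue item 9. An eligibility rule has to be auditable as written, nothing else in the protocol corrects this one, and the remaining screens do not replace a performance-status limit.

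**Conclusion.** The point holds for item 9 and should be corrected. Under the logical reading the item excludes none of the ten Karnofsky levels. Under the either-scale reading, the WHO half admits 6 or 7 of the ten levels, all at the less fit end, and refuses WHO 0 and 1. This rests on the standard direction of the two scales. The count of levels rests also on the three assumed conversions, but the opposition between the two halves does not depend on any of them.

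The consequence is confined to screening and to the description of the study population. No sample size, test or estimate in the plan changes. Exclusion 2 is a minor wording matter whose meaning can be inferred from context.

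**What to change.** 1. The sponsor should reconcile the two halves of item 9 so that both limits point in the same direction and correspond to the same fitness level. The investigators should set the WHO value. Reversing the sign alone may not be enough (step 2 of the working), so the conversion used should be stated, or a single scale named. The symbol should be checked against the source page first.
2. Check patients already enrolled under this criterion against the corrected item, and report any who do not meet it.
3. As a wording note, reconcile exclusion 2 with inclusion groups 1 to 4 by stating whether it refers to disease outside the liver. The documents give no ground for changing the scope of its reference to diffuse disease at the same time.

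The cost is a wording amendment and a review of existing records. No patients, visits or procedures are added.
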